| Sample Size Considerations | The study will test the hypothesis that patients undergoing endovascular revascularization will show shift in the distribution of scores on the mRS scale at 90 days, assuming that categories 5 and 6 (bedbound with severe disability, and death) are collapsed, and the effect leads to an assumed common odds ratio of 1.8. The predicted sample size is 500 patients, allowing for potential cross-over and drop-outs.   |
| Randomization              | Randomization will use a minimal sufficient balance algorithm to ensure balance within groups on important predictors of outcome including age, baseline stroke severity, initial arterial lesion location, ASPECTS score and site. We will have suggested time quotas for treatment: CT-to-randomization: 15 minutes; Randomization-to-puncture: 30 minutes; Puncture-to-recanalization: 30 minutes; we will aim to meet this time quotas by ongoing training of the sites and by choosing sites a priori that can meet these targets. |
| Analysis                   | The primary analysis will be an intention to treat analysis. It will use an ordinal logistic regression model to derive the common odds of improvement (“shift”) along the mRS scale. The proportional odds assumption will be testing using a Brant test. The analysis will be adjusted for the 6 variables used for minimization (age, sex, NIHSS score, ASPECTS score, occlusion location, intravenous tPA use).   |
| Consent                    | Waiver/deferral of consent when necessary and where possible according to local IRB approval. Assent or informed consent at other sites. Consent must be obtained within the proposed time targets.   |

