### Statistical Considerations

The primary outcome will be a shift or one or more categories (proportional odds analysis) on the modified Rankin scale determined at 90 days from randomization.

The primary hypothesis is:

HA: Subjects in the intervention arm will have a 1.8-fold greater odds of showing improvement on the mRS at 90 days.

[figure not shown]
The primary analysis will be an intention to treat analysis. It will use an ordinal logistic regression model to derive the common odds of improvement (“shift”) along the mRS scale. The proportional odds assumption will be testing using a Brant test. The analysis will be unadjusted. A secondary analysis using a proportional odds model adjusted for the 6 variables used for minimization (age, sex, NIHSS score, ASPECTS score, occlusion location, intravenous tPA use) will be reported.

A total sample size of 188 ideal patients per group with 90% power is required with alpha at 0.05. The sample size calculation is based upon Whitehead’s power formula. The sample size is estimated without the knowing the distribution of pre-specified confounding variables. We assume no cross-overs. Allowing for losses-to-follow-up (of up to 6%, n=24/400), a total required sample size of 400 ideal patients is anticipated. However, we know that the effect size is highly dependent upon very rapid treatment times and have planned to continue enrolling patients until up to 200 endovascular patients have been treated with a CT-to-first reperfusion time < 90 minutes. We conservatively assume that patients treated later than this time window have show no treatment effect. Currently, in our initial patients we are meeting this quality metric in 60% of our patient population, compared to our desired 80% or greater. Therefore,

- (1) the trial is powered to detect an effect size based upon 400 ideal patients
- (2) the maximum sample size for the trial will be 500 patients to ensure that 200 patients in the endovascular group meet the target treatment times (ie. are ideal patients).

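### The stated 90% power is for a comparison of ideal patients only; under the planned intention-to-treat analysis with 500 randomised, the protocol's own no-effect assumption gives about 82% at its 80% timing target and about 58% at the 60% it reports.

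*Protocol*

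**What the plan says.** The sample size is in the protocol's Statistical Considerations section: "A total sample size of 188 ideal patients per group with 90% power is required with alpha at 0.05". The synopsis gives the effect size ("the effect leads to an assumed common odds ratio of 1.8") with mRS categories 5 and 6 combined. An allowance of up to 6% for loss takes 376 to 400 ideal patients.

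The section then recognises that some endovascular patients will be reperfused later than 90 minutes after CT: "We conservatively assume that patients treated later than this time window have show no treatment effect". On attainment it says: "Currently, in our initial patients we are meeting this quality metric in 60% of our patient population", against a desired rate of at least 80%. It concludes that the trial is powered on 400 ideal patients and sets a maximum of 500, so that 200 endovascular patients meet the timing target.

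The same section fixes the analysis set: "The primary analysis will be an intention to treat analysis".

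The synopsis differs on two points. Its Population entry lets recruitment continue until 200 endovascular patients meet the target, with no upper limit. Its Sample Size Considerations entry says: "The predicted sample size is 500 patients, allowing for potential cross-over and drop-outs". The statistics section says "We assume no cross-overs" and justifies the extra 100 patients by late treatment.

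**The concern.** An intention-to-treat comparison keeps every randomised endovascular patient. If late-treated patients gain nothing, the arm's average effect is smaller than an odds ratio of 1.8, however many ideal patients it also contains. Recruiting until 200 are ideal adds patients but leaves the late ones in.

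The protocol describes no comparison of 188 ideal patients with 188 ideal patients, and none could be formed directly: control patients have no CT-to-reperfusion time that would make them ideal. The 90% therefore describes a test that will not be run.

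At stake is how a neutral result is read. If the trial is thought to have a 10% chance of missing the effect when the chance is nearer 18% or 42%, a neutral finding carries more weight than it should.

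**Working it through.** **Inputs.** From the protocol: odds ratio 1.8; six mRS categories; 1:1 allocation; alpha 0.05; power 90%; loss 6%; no effect in late-treated patients; attainment 60% now and at least 80% desired; 500 randomised. Assumed: a two-sided test (sidedness is not stated), an unadjusted analysis, and the mRS distribution, which the protocol gives only in a figure that is not available. Six equal pooled proportions are used, with a check over other distributions below.

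**Reproducing the stated size.** Whitehead's formula for 1:1 allocation is

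N = 12(z₁₋α/₂ + z_power)² / [(ln OR)² (1 − Σp̄³)].

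With 1.960 + 1.282, ln 1.8 = 0.588 and 1 − 6/216 = 0.972, N = 375, against 376 stated (2 × 188). Then 376/0.94 = 400. Both figures reproduce. A one-sided test would give about 306, so the stated size implies a two-sided test.

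**Power of the planned analysis.** Let a be the share of the endovascular arm that meets the target. The diluted log odds ratio is approximately a × ln 1.8, and

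power = Φ( √(N × 0.972/12) × a × 0.588 − 1.960 ).

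With 500 randomised, N = 500 × 0.94 = 470 evaluable and √(470 × 0.972/12) × 0.588 = 3.627.

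| Attainment a | 3.627a − 1.960 | Power, 500 randomised |
|---|---|---|
| 60% | 0.216 | 58.6% |
| 80% | 0.942 | 82.7% |
| 85% | 1.123 | 86.9% |
| 90% | 1.304 | 90.4% |
| 100% | 1.667 | 95.2% |

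**Check by simulation.** 20,000 simulated trials per scenario used an explicit mixture (share a at odds ratio 1.8, the rest at 1.0), a tie-corrected Wilcoxon test and four assumed control distributions. They gave 57.1–57.7% at 60% attainment, 81.7–82.2% at 80% and 89.8–90.0% at 90%. The unknown mRS distribution hardly matters.

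**Why 500 is not enough.** 400/0.8 = 500 restores the count of ideal patients. Because required size varies with the inverse square of the log odds ratio, dilution needs 1/a²: 376/0.8² = 588 evaluable, or 625 randomised, at 80%; and 376/0.6² = 1,044 evaluable, or about 1,111 randomised, at 60%.

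**If enrolment stops at 200 ideal endovascular patients.**
- 100% attainment: 400 randomised, power 90%.
- 90%: 400/0.9 = 444 randomised, 418 evaluable, power about 87%.
- 80%: 500 randomised, power about 82%.
- 60%: 250 × 0.6 = 150 ideal endovascular patients at the cap of 500, not 200. Reaching 200 takes 400/0.6 = 667 randomised, which the synopsis would allow, and power is then about 71%.

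**The case against.** Several counter-arguments are fair.

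- **The odds ratio of 1.8 may be meant for the whole arm.** The hypothesis in Statistical Considerations attaches it to the intervention arm without qualification. On that reading 500 patients give about 95% power. But this conflicts with the no-effect assumption and with the ideal-patient basis of the calculation in the same section. The ambiguity stands and needs resolving.
- **No effect in late patients is a deliberately cautious assumption, and 60% comes from early patients.** The Speed of Intervention section provides training, quarterly feedback and removal of sites that miss targets. So 58% is a scenario, not the expected power. Still, the cautious assumption was never carried into the stated power, so it gives no protection.
- **The analysis is not settled.** The synopsis makes the primary analysis adjusted; Statistical Considerations makes it unadjusted. Adjustment could change power, so the figures here are for the unadjusted model.
- **The stated arithmetic is right.** The figures 188 and 400 reproduce, and 500 equals 400/0.8. The fault is that they do not describe the planned test.

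A reader might infer that 82% is the best the trial can do, or that 90% requires every patient to be ideal. The protocol does not support either. Its target is 80% or more, and with 500 enrolled power returns to about 90% at 90% attainment. The 82% also uses the full 6% loss allowance; with no losses it is about 85%. Only if enrolment stops at 200 ideal endovascular patients does 90% require full attainment.

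**Conclusion.** The point holds in conditional form. The 90% is the power for 188 against 188 ideal patients, not for the intention-to-treat test the protocol plans. With odds ratio 1.8 in ideal patients, no effect in the rest, two-sided alpha 0.05, an unadjusted analysis, 500 randomised and 6% loss, power is about 82% at 80% attainment, 58% at 60%, 90% at 90% and 95% at 100%. The chance of missing the effect is thus about 18% at the lower edge of the target and about 42% at the reported rate.

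Two related statements also fail: a cap of 500 does not secure 200 ideal endovascular patients unless attainment is at least 80%, and the synopsis and statistics section disagree on whether 500 is a maximum and whether it covers cross-over. The cross-over conflict is minor. None of this affects type I error or the validity of the planned comparison.

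**What to change.** In Statistical Considerations:

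- State the power for the intention-to-treat analysis as conditional on attainment. For example: with 500 randomised and 6% loss, power is about 82% if 80% of the endovascular arm meets the timing target, about 58% if 60% does and about 90% if 90% does, assuming no effect in the remainder, a two-sided 5% test and no covariate adjustment.
- Say that the calculation for 400 ideal patients is not the power of the primary analysis.
- State whether the odds ratio of 1.8 refers to ideal patients or to the whole arm, and that alpha is two-sided if that is intended.
- Remove the claim that 500 patients ensure 200 ideal endovascular patients.

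Across the synopsis and Statistical Considerations, reconcile whether 500 is a maximum and whether it allows for cross-over. If the primary analysis is to be adjusted, as the synopsis has it, say so and note that the power figures are for the unadjusted model.

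The cost is rewording and a less favourable stated power. No extra patients are needed to make the statement correct.

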## Protocol synopsis

|                            |  |
|----------------------------|--|
| Objectives          | 
The primary objectives of this study are to show that rapid endovascular revascularization amongst radiologically selected (small core/proximal occlusion) patients with ischemic stroke results in improved outcome compared to patients treated in clinical routine.
 
The secondary objectives of this study are to demonstrate the safety and feasibility of achieving rapid endovascular revascularization in this population of patients (<60 min CT-groin puncture ('Picture-to-puncture time'); <90 min CT-recanalization).
  |
| Experimental Design | A Phase 3, randomized, open-label with blinded outcome evaluation, controlled, parallel group design.  |
| Population          | 
500 male and female patients; additional subjects may be recruited until 200 subjects randomized to endovascular arm achieve CT-to-recanalization <90 minutes.
 
Inclusion Criteria
 
 
1. Acute ischemic stroke
 
2. Age 18 or greater
 
3. Onset (last-seen-well) time to randomization time < 12 hours.
 
4. Disabling stroke defined as a baseline NIHSS > 5 at the time of randomization.
 
5. Pre-stroke (24 hours prior to stroke onset) independent functional status in activities of daily living with modified Barthel Index > 90. Patient must be living in their own home, apartment or seniors lodge where no nursing care is required.
 
6. Confirmed symptomatic intracranial occlusion, based on single phase, multiphase or dynamic CTA, at one or more of the following locations: Carotid T/L, M1 MCA, or M1-MCA equivalent (2 or more M2-MCAs). Anterior temporal artery is not considered an M2.
 
7. Non-contrast CT/CTA for trial eligibility performed or repeated at ESCAPE stroke center with endovascular suite on-site.
 
8. Endovascular treatment intended to be initiated (groin puncture) within 60 minutes of baseline non-contrast CT with target CT to first recanalization of 90 minutes.
 
 |

9. Signed informed consent or appropriate signed deferral of consent where approved.

Exclusion Criteria

1. Baseline non-contrast CT reveals a moderate/large core defined as extensive early ischemic changes of ASPECTS 0-5 in the territory of symptomatic intracranial occlusion.

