## Background

The rationale for this study is the following –

- 1) There is no convincing, randomized trial evidence that modern endovascular therapy is better than routine care, including routine intravenous thrombolysis, for acute ischemic stroke. There is nevertheless, strong evidence that endovascular therapy can result in faster, more complete recanalization and that this should result in better stroke outcomes.
- 2) Modern acute endovascular therapy has advanced to a stage where testing is now possible because complication rates are very low and technology is both increasingly operator independent and expertise is widespread.
- 3) The mismatch hypothesis (MR perfusion-diffusion or CT perfusion-CBV) has not been shown to be useful for making treatment decisions in large part because of

the time-trade off between the time required to gather information and the imperative to treat quickly.

- 4) Substantial variation in subject susceptibility to infarction makes average time limits for thrombolysis, derived from clinical trials, less relevant to individual patients.
- 5) Patients with a small core of infarct but a significant clinical deficit benefit from reperfusion even at late time windows after treatment.
- 6) Up to 25% of ischemic stroke patients awake with stroke symptoms, have an unwitnessed time of onset, have an ischemic stroke as a complication of a surgical procedure, have an ischemic stroke despite treatment with anticoagulants and are therefore not eligible for routine chemical thrombolysis with IV tPA.
- 7) Patients with large vessel occlusions frequently do not recanalize fast enough with intravenous chemical thrombolysis (eg. tPA).
- 8) Endovascular thrombectomy results in very high recanalization rates of about 80%.
- 9) There is a compelling need to evaluate patients who are not currently treated with thrombolytic therapy (chemical or mechanical) and to use these groups to demonstrate that endovascular therapy is an effective treatment modality for acute ischemic stroke.

Two key concepts will be evaluated in this trial:

- (i) Revascularization of patients with large vessel occlusion and small core, good collaterals will result in a greater proportion of patients with a good outcome
- (ii) Endovascular revascularization can be done with a CT to TIC13 flow in < 90 minutes.

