### Study Enrolment Process

Patients will be identified using usual standard of care screening methods at the acute stroke hospital. This will include screening by neurology residents, fellows, nurse practitioners, physician assistants or faculty physicians. Sites will only be selected to participate in the study if they have intact mechanisms for screening this population of patients. This includes standard of care use of CT angiography among stroke patients. All patients will undergo an acute clinical assessment, blood laboratory assessment and baseline brain imaging with acute CT and CTA. CT perfusion or MR imaging are not mandated in the study, but not prohibited. However from the perspective of imaging to recanalization time, the first slice of the baseline non-contrast CT is when the clock starts. It is mandated that a CT perfusion cannot be performed before the CTA.

If the patient remains eligible after completion of routine screening, the patient will be consented (as required) and enrolled into the study. The patient is considered enrolled into the study once the randomization assignment has been received (eg. study number assigned over the internet). A patient who consents but is not randomized will be considered a screen failure.

Treatment will be assigned using 1:1 randomization. Randomization will be conducted using a web-based algorithm with treatment assignment allocated by web-based real-time interaction with the site. The initial randomization of the first 40 patients will be completed using randomly ordered permuted blocks of 4 or 6 and assigned by site. Thereafter randomization, subject data will be entered into an on-line database within 6 hours of patient enrolment. A minimal sufficient balance method will be used to ensure that the patients entered into the trial will be matched between control and active treatment arms on the key variables of site, age, sex, baseline NIHSS score, baseline NCCT ASPECTS score, and location of the symptomatic target arterial occlusive lesion. This method will ensure that by the end of the trial, the patients are well matched for important prognostic variables and therefore that by chance, the groups are not unbalanced on one particular variable.

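### The protocol both caps enrolment at 500 and allows it to run past 500, and the cap delivers 200 on-target endovascular patients only at the hoped-for 80% rate, not the 60% it reports

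*Protocol*

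**What the plan says.** The size of the trial is described in three places in the protocol.

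- **Protocol synopsis, Population.** The number is 500, but "additional subjects may be recruited until 200 subjects randomized to endovascular arm achieve CT-to-recanalization" in under 90 minutes. No upper limit is given.
- **Statistical Considerations, closing list.** Here 500 is a ceiling: "the maximum sample size for the trial will be 500 patients to ensure that 200 patients in the endovascular group meet the target treatment times". The paragraph before the list words it differently: the investigators "have planned to continue enrolling patients until up to 200 endovascular patients have been treated with a CT-to-first reperfusion time" below 90 minutes.
- **Protocol synopsis, Sample Size Considerations.** Again 500, but explained as an allowance for cross-over and drop-out. Statistical Considerations assumes no cross-overs and ties 500 to treatment times.

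The base calculation is: "A total sample size of 188 ideal patients per group with 90% power is required with alpha at 0.05". Allowing up to 6% loss brings this to 400. Patients treated outside the time window are assumed to gain nothing, and the primary analysis is by intention to treat. On attainment so far: "Currently, in our initial patients we are meeting this quality metric in 60% of our patient population, compared to our desired 80% or greater". On allocation, Study Enrolment Process says: "Treatment will be assigned using 1:1 randomization".

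**The concern.** A reader cannot tell when enrolment ends. Under one section the trial stops at 500 whatever the count of on-target patients; under the other it continues until the count is reached, however many that takes. The rule is stated, and stated inconsistently, so this is not a detail that can be left to a statistical analysis plan.

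The cap is also presented as a guarantee of 200 on-target endovascular patients, although the figure of 500 follows only from the desired attainment rate and the rate reported a few lines earlier is well below it.

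Power is at stake too. The 90% is computed for patients who all receive timely treatment. The trial will randomise and analyse late-treated patients as well, and the protocol assigns them no benefit. No power is given for that mixed population.

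Finally, the counted event is called recanalization in the synopsis and first reperfusion in Statistical Considerations. If these are graded differently, the count of 200 is reached at different times.

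**Working it through.** **Inputs.** From the protocol: common odds ratio 1.8; alpha 0.05; 90% power; Whitehead's formula; mRS 5 and 6 collapsed (six categories); up to 6% loss; 1:1 allocation; attainment 60% observed and 80% desired; no effect in late-treated patients. Assumed: two-sided alpha; six equal mean category probabilities, because the figure with the projected distribution is not shown; exactly 250 patients in the endovascular arm; a constant attainment rate.

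**1. The protocol's own figures reproduce.** Whitehead: n per group = 6(z₀.₉₇₅ + z₀.₉₀)² / [(ln 1.8)² (1 − Σp̄³)].
- ln 1.8 = 0.5878, and 1 − 6 × (1/6)³ = 0.9722.
- n = 6 × (1.960 + 1.282)² / (0.3455 × 0.9722) = 187.7, so 188 per group.
- Two illustrative skewed distributions give 189 and 192. A one-sided test gives 153, so the calculation was evidently two-sided.
- 2 × 188 = 376, and 376 / 0.94 = 400.

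**2. Where 500 comes from.** Total needed = 2 × 200 / rate. At 80% this is 2 × 200 / 0.80 = 500, so the cap embodies the desired rate.

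**3. What 500 delivers.** The endovascular arm has about 250 patients. The chance of at least 200 on target is the upper tail of Binomial(250, rate).

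| Attainment | Expected on target of 250 | Chance of ≥ 200 | Total needed on expectation |
|---|---|---|---|
| 60% | 150 | about 1 in 10¹¹ | 667 |
| 70% | 175 | 0.02% | 571 |
| 75% | 187.5 | 3.7% | 533 |
| 80% | 200 | 54% | 500 |
| 85% | 212.5 | 99% | 471 |

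A 95% chance of 200 within 250 needs a true rate of about 84%.

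**4. Intention-to-treat power at 500.** With 6% loss, 470 are analysed. Information V = 470 × 0.9722 / 12 = 38.08, and √V = 6.171. With no effect in late-treated patients, the average log odds ratio is roughly rate × ln 1.8, and power = Φ(log odds ratio × √V − 1.96).
- 80% attainment: 0.8 × 0.5878 = 0.470; 0.470 × 6.171 = 2.902; Φ(0.942) = 82.7%.
- 60% attainment: 0.6 × 0.5878 = 0.353; 0.353 × 6.171 = 2.176; Φ(0.216) = 58.6%.

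Mixing the shifted and unshifted outcome distributions directly, instead of scaling the log odds ratio, gives 82.5% and 58.4%. The same formula with 376 analysed and full effect returns 90.0%, so the drop comes from dilution.

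**5. Reaching 200 on target does not restore 90% either.** At 60% attainment and 668 randomised (334 per arm), about 628 are analysed: V = 628 × 0.9722 / 12 = 50.9, √V = 7.13, 0.353 × 7.13 = 2.516, and Φ(0.556) = 71%. The late-treated patients remain in the comparison.

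**The case against.** The best defence is that 60% is an early figure and not a forecast. Speed of Intervention describes site selection on past performance, quarterly training and feedback, and removal of sites that miss the targets. At the stated goal of 80%, 500 is exactly the expected requirement. This stands: the very small probability at 60% should not be read as a prediction, because it assumes that the early rate persists. But at exactly 80% the odds of reaching 200 are only about even, so a guarantee is still too strong.

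It can also be said that the synopsis clause is permissive and that 500 appears in every account. That narrows the contradiction but does not remove it: an extension without limit is incompatible with a maximum.

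Two stronger readings are tempting and are not supported.

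- *That 80% attainment is out of reach because recanalisation rates cap it.* The Background quotes about 80%, and the table of device studies gives 68.5% for one stent retriever. But the text below that table reports 80% or more in both stent-retriever studies, and the grades behind those rates are not given. First reperfusion may be a looser threshold, so no ceiling is shown. The complete-flow wording in the Background is a concept to be evaluated, not the enrolment count.
- *That tying enrolment to an event seen in one arm of an open-label trial biases the result.* The trigger is a process time, not a comparison of outcomes. Simulation under no treatment effect, stopping at the 200th on-target patient with fast reperfusion prognostic by 0 to 1 SD of a normal outcome, gave two-sided type I error of 4.9% to 5.3%. No inferential harm is demonstrated.

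**Conclusion.** The concern holds in three parts. The enrolment rule contradicts itself between the synopsis and Statistical Considerations. The claim that a cap of 500 secures 200 on-target endovascular patients is wrong as written: it needs 80% attainment, gives about a 54% chance even then, and yields about 150 at the reported 60%. And the stated 90% power belongs to 400 ideal patients; for 500 randomised under the protocol's own dilution assumption it is about 82 to 83% at 80% attainment and 58 to 59% at 60%.

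The contradiction and the expected counts rest on the document and simple arithmetic. The probabilities assume a constant rate and exactly 250 in the endovascular arm. The power figures also rest on two-sided 0.05, six equal categories, 6% loss and no benefit at all after 90 minutes. That last assumption is the protocol's own and is described there as conservative; any benefit in late-treated patients would raise the power. The base figures of 188 per group and 400 in total are not in error.

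**What to change.** - State one enrolment rule with one maximum, in the same words, in the synopsis and in Statistical Considerations. One option is 500 as the total randomised, deleting the open-ended extension clause. Another is to stop at 200 on-target patients or 500 randomised, whichever comes first. If the sponsor prefers to extend, a higher stated maximum is needed.
- Replace the guarantee with the attainment rate assumed (80%) and the number expected from it (200 of about 250).
- Restate intention-to-treat power for 500 randomised at that rate, preferably with a lower rate alongside, using the projected mRS distribution that the sponsor holds. Give one reason for 500 in both sections.
- Use one defined term for the counted event in both places. Time zero needs no new decision: Study Enrolment Process and Speed of Intervention already set it at the first slice of the baseline non-contrast CT.

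The cost is wording and one recalculation. The sponsor gives up the unlimited extension and reports a less favourable power figure. If 500 becomes a fixed total, it also gives up a possible stop below 500, at about 471 (400 / 0.85) with 85% attainment; the whichever-first rule keeps that.
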